7.4. Reporting Procedures – Notifying the IRB

7.4.1. Adverse Event Reporting

Adverse events will be reported to the investigators, the involved subject, the IRB, and to LiveMetric within 24 hours of the event.

7.4.2. Serious Adverse Event Reporting

Serious adverse events will be reported to the investigators, the involved subject, the IRB, and to LiveMetric within 24 hours of the event.

7.4.3. Unanticipated Problem Reporting

Incidents or events that meet the OHRP criteria for UPs require the creation and completion of an UP report form. It is the site investigator's responsibility to report UPs to their IRB and to the DCC/study sponsor. The UP report will include the following information:

- Protocol identifying information: protocol title and number, PI's name, and the IRB project number;
- A detailed description of the event, incident, experience, or outcome;

- An explanation of the basis for determining that the event, incident, experience, or outcome represents an UP;
- A description of any changes to the protocol or other corrective actions that have been taken or are proposed in response to the UP.

To satisfy the requirement for prompt reporting, UPs will be reported using the following timeline:

- UPs that are SAEs will be reported to the IRB and to the DCC/study sponsor within <insert timeline in accordance with policy> of the investigator becoming aware of the event.
- Any other UP will be reported to the IRB and to the DCC/study sponsor within <insert timeline in accordance with policy> of the investigator becoming aware of the problem.
- All UPs should be reported to appropriate institutional officials (as required by an institution's written reporting procedures), the supporting agency head (or designee), and OHRP within<insert timeline in accordance with policy> of the IR's receipt of the report of the problem from the investigator.

7.5. Reporting Procedures – Notifying the Study Sponsor

The study clinician will complete a SAE Form within the following timelines:

- All deaths and immediately life-threatening events, whether related or unrelated, will be recorded on the SAE Form and submitted to the DCC/study sponsor within 24 hours of site awareness. See Section 1, Key Roles for contact information.
- Other SAEs regardless of relationship will be submitted to the DCC/study sponsor within 72 hours of site awareness.

All SAEs will be followed until satisfactory resolution or until the site investigator deems the event to be chronic or the adherence to be stable. Other supporting documentation of the event may be requested by the DCC/study sponsor and should be provided as soon as possible.

As a follow-up to the initial report, within the following 48 hours of awareness of the event, the investigator shall provide further information, as applicable, on the unanticipated event or the unanticipated problem in the form of a written narrative. This should include a copy of the completed Unanticipated Problem form, and any other diagnostic information that will assist the understanding of the event. Significant new information on ongoing unanticipated adverse effects shall be provided promptly to the study sponsor.

The study investigator shall complete an Unanticipated Adverse Device Effect Form and submit to the study sponsor and to the reviewing IRB as soon as possible, but in no event later than 10 working days after the investigator first learns of the effect. The study sponsor contact information is provided in Section 1, Key Roles.

As a follow-up to the initial report, within the following 48 hours of awareness of the event, the investigator shall provide further information, as applicable, on the unanticipated event or the unanticipated problem in the form of a written narrative. This should include a copy of the completed Unanticipated Problem form, and any other diagnostic information that will assist the understanding of the event. Significant new information on ongoing unanticipated adverse effects shall be provided promptly to the study sponsor.

The study sponsor is responsible for conducting an evaluation of an unanticipated adverse device effect and shall report the results of such evaluation to FDA and to all reviewing IRBs and participating investigators within 10 working days after the sponsor first receives notice of the

effect. Thereafter the sponsor shall submit such additional reports concerning the effect as FDA requests.

7.6. Study Halting Rules

If any SAE occurs, during the study, the study will be stopped.

7.7. Safety Oversight

It is the responsibility of the Principal Investigator to oversee the safety of the study at his/her site. This safety monitoring will include careful assessment and appropriate reporting of adverse events as noted above, as well as the construction and implementation of a site data and safety-monitoring plan. Medical monitoring will include a regular assessment of the number and type of serious adverse events.

8. Clinical Monitoring

PI will be conducting monitoring to ensure safety of subjects.

9. Statistical Considerations

Data from the A-line monitor and from the LiveMetric device shall be collected and processed using a validated Software. Categorical parameters shall be presented in percentages and will be compared using X² testing. Continuous variables shall be reported as mean \pm standard deviation and will be compared using the Student's t-test. Correlation shall be determined via linear regression analysis. Agreement shall be determined via the Bland and Altman technique. The analysis shall be conducted for intermittent values by applying the reference ISO 81060-2:2013.

The LiveMetric device shall provide values for each intermittent session and shall be compared to a range measured by the A-Line (data point). The data point is defined as the interval between the lower and higher value read by the A-Line, providing: the interval is no less than 30 seconds; the difference range from the reference device is less than the permissible highest range of 20 mmHg for SYS and 12 mmHg for DIA. Should the LiveMetric device read within the same range as the A-line, then the reading is considered accurate. However, if the reading is not within the defined range, then the error rate is defined as the range in mmHg between the closest edges of the reference reading to the values obtained by the LiveMetric device

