4.1. Description of Study Design

1. A medical professional will measure simultaneous non-invasive auscultatory readings to determine the lateral difference for later adjustment of calculation accordingly. Calculation of lateral difference is provided in section (**Error! Reference source not found.**). All data from a subject shall be excluded if: i) the lateral difference of the reference systolic BP readings is more than 15 mmHg (2,00 kPa); or ii) the lateral difference of the reference diastolic BP readings is more than 10 mmHg (1,33 kPa).
2. If subject's reading is eligible, the medical professional or research personnel will place the LiveMetric wristband on the opposite limb than the one having the A-line, providing the location of the placement has intact skin.
3. During the measurement stage, BP values are simultaneously recorded from the reference invasive A-line and the LiveMetric device. In addition, other vital signs from the monitoring equipment can be collected as available (ECG, Respiratory rate, Pleth, and HR). The invasive BP values and other vital signs are captured from the Vital Signs Monitor (available in the patient's room) and the LiveMetric device. A measurement session of 30 minutes will be conducted for each subject. During the measurements, no information from the device will be provided to the investigator or study personnel. All the data will be processed and analyzed post-measurement according to the following considerations as required by the standard: only up to 10 consecutive measurements per subject will be analyzed; measurement will be made over 30 seconds of recording; consecutive meas-

urement will be considered as the next 30 seconds following at least a 60 second interval. Measurement (data points) is defined as recording or acquisition of signal from the monitor. The medical professional will take off the wristband at the end of this process.

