9.1. Statistical and Analytical Plans (SAP)

Baseline demographics including age, weight, current medications, and general medical condition will be collected anonymously.

For each of the subjects, 10 intra-arterial blood pressure measurements will be collected and 10 wristband measurements will be collected at the same time points.

Systolic blood pressure measurements will be compared using an acceptable standard deviation of 10 mm Hg (\pm 5 mm Hg).

Diastolic blood pressure measurements will be compared using an acceptable standard deviation of 10 mm Hg (\pm 5 mm Hg).

Mean arterial pressure measurements will be compared using an acceptable standard deviation of 5 mm Hg (+/- 2.5 mm Hg).

The percentage of blood pressure measurements falling within the acceptable standard deviation will be compared.

The percentage of blood pressure measurements for each patient falling within the acceptable standard deviation will also be compared.

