9.3.1. Determining the reference BP

The invasive SYS and DIA BP values shall be determined from the recordings. (The BP reading will be recorded beat to beat, without any averaging, from the A-line and from the LiveMetric device). The mean and experimental standard deviation of the SYS and DIA BP from the recordings will be determined.

Since there is no cuff inflation interruption by the LiveMetric device, the A-line ranges shall be determined from the recording for a duration of 30 seconds, while simultaneously recording the same period of the data point from the LiveMetric device.

The reference SYS is defined as the range of a ± 1 experimental standard deviation around the mean value of the invasive systolic BP values obtained during the data point range performed by the LiveMetric device. The reference DIA BP is defined as the range of ± 1 experimental standard deviation around the mean value of the invasive diastolic BP values obtained during the same period.

Isolated VPB's shall be addressed by removing the pressure pulse associated with the VPB and the following compensatory beat.

If the value obtained from the LiveMetric determination lies within the range of the reference BP as determined in (**Error! Reference source not found.**), assign an error of 0 mmHg (0 kPa) to this determination.

If the value obtained from the LiveMetric determination lies outside the range of the reference BP as determined in (**Error! Reference source not found.**) subtract the value of the determination from the adjacent limit of the range of the variation of BP. That difference represents the error for this determination.

The arithmetic mean of the error is calculated and its experimental standard deviation from the errors of each recording for each BP value (SYS & DIA) and determination for each patient.

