9.3.3. Data Analysis

The data set will be collected for clinical investigation purposes and will be processed and analyzed according to the formulas provided in the ISO 81060-2: 2013.

The lateral difference will be calculated initially as the average difference between the readings or determination made on each limb according to Formula:

$$LD = \frac{1}{3} \times \left(\sum_{i=1}^3 P_i - \sum_{j=1}^3 P_j \right);$$

i is the index for the determination on the limb used for the sphygmomanometer-under-test determination;

j is the index for the reading on the limb used for the reference reading.

Only data within the inclusion criteria as defined in section (**Error! Reference source not found.**) will be processed for the purpose of clinical investigations.

The mean value of the errors for SYS and DIA BP, \bar{x}_n of the n individual paired determination of the LiveMetric device as determined above for all subjects, will be calculated according to Formula:

$$\bar{x}_n = \frac{1}{n} \times \sum_{j=1}^n X_1$$

and Formula:

$$S_n = \sqrt{\frac{1}{n-1} \times \sum_{j=1}^n (X_i - \bar{x}_n)^2}$$

Where;

X_1 is the error of the ith individual determination as determined in (**Error! Reference source not found.**);

n is the total number of determinations;

i is the index for the individual determination.

Mean or standard deviation outside the specified ranges above, mandate further algorithm modification until subsequent testing with new data sets done in accordance with this protocol meets the above criteria.

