9.3.4. Analysis of the Primary Efficacy Endpoint

Primary Endpoint is determined by meeting the success criterion for SYS and DIA BP as defined by ISO 81060-2: 2013

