9.5. Sample Size

As determined in ISO 81060-2 / 2013; a reference invasive BP monitoring equipment clinical investigation shall consist of a minimum of 15 patients. For each patient shall be a minimum of 150 valid BP measurements in the clinical investigation.

The goal sample size is 15 patients. It is expected that 25 patients will need to be screened to obtain the desired sample size.

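### Section 9 names a t-test, chi-squared test, regression and Bland-Altman without stating pairing or unit, and nothing in the plan allows for repeated readings within patients; minor, because only supporting analyses are affected

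*Combined protocol and SAP*

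**What the plan says.** The opening paragraph of Section 9 lists four methods. Categorical parameters get a chi-squared test. Continuous variables "will be compared using the Student's t-test. Correlation shall be determined via linear regression analysis". Then "Agreement shall be determined via the Bland and Altman technique". The paragraph does not name the groups being compared, whether the t-test is paired, or whether the unit is the reading or the patient.

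The data structure is given elsewhere:

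- Section 4.1: "only up to 10 consecutive measurements per subject will be analyzed", from one 30-minute session, each over 30 seconds and at least 60 seconds apart.
- Section 9.1: ten A-line readings per subject, and "10 wristband measurements will be collected at the same time points".
- Section 9.5: the investigation "shall consist of a minimum of 15 patients", and 15 is the goal.

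Three places touch on pairing or unit, each for its own quantity only:

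- Section 9.3.3 computes the mean and SD of the paired errors over all subjects, where "n is the total number of determinations".
- Section 9.3.1 says "The arithmetic mean of the error is calculated and its experimental standard deviation from the errors of each recording", and mentions each patient.
- Section 9.1 adds a per-patient percentage within tolerance.

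None of these is tied to a test, an interval or a model for repeated readings. Section 9.3.4 sets the decision rule: "Primary Endpoint is determined by meeting the success criterion for SYS and DIA BP", as defined by ISO 81060-2:2013.

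**The concern.** Ten readings taken within half an hour share one wrist, one device placement and one left-right pressure difference, so their errors are likely to be correlated. With 15 patients, the information about average bias lies somewhere between 15 and 150 independent observations. The Section 9 list leaves open at least three t-tests, and they behave differently:

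- A paired test on patient means is valid.
- A paired test on pooled differences rejects too often when there is no bias.
- An unpaired test on pooled readings carries the spread of blood pressure between patients in its error term and can miss a real bias.

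The same data could therefore be reported as showing a bias or not, depending on a choice that the plan does not fix in advance. An interval for mean error or for a limit of agreement, if computed from pooled readings, would claim more precision than 15 patients can give.

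**Working it through.** **The plan's own figure.** 15 patients × 10 readings = 150. This matches the 150 in Section 9.5 only as a study total. That section words it per patient, which conflicts with the limit of 10 in Section 4.1 and should be reconciled separately. The plan gives no alpha, power, SD or ICC, so there is no power calculation to reproduce.

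**Inputs.** From the documents: 15 patients, and 10 pairs each (the maximum). Assumed: ICC of the error 0.1, 0.3 or 0.5; error SD 8 mmHg unless stated; within-patient BP SD 5; between-patient BP SD 10, 15 or 20. Results marked (sim) come from simulated trials with normal patient effects and normal residuals.

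**Design effect.** 1 + (10 − 1) × ICC = 1.9, 3.7, 5.5. The 150 pairs are worth 150/1.9 = 78.9, 150/3.7 = 40.5 and 150/5.5 = 27.3 independent pairs.

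**Pooled paired t-test, no true bias.** The pooled standard error is too small by √1.9 = 1.38, √3.7 = 1.92 and √5.5 = 2.35. The 1.96 threshold then acts as 1.96/1.38 = 1.42, 1.02 and 0.84, which gives a two-sided error of about 15%, 31% and 40%. Simulation gives 15%, 31% and 41%, against about 5% on patient means. The error SD cancels, so this holds for any SD. On the Section 9.3.1 error, which is zero inside the reference range, an assumed ±5 range gives 14%, 29% and 39% (sim).

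**95% interval for mean error.**

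- Pooled: t(149) × SD/√150 = 1.976 × 8/12.25 = 1.29 mmHg.
- Patient means: t(14) × SD × √(design effect/150) = 2.145 × 0.653 × 1.38, 1.92 or 2.35 = 1.93, 2.69, 3.29. The average over trials is 1.9, 2.6 and 3.2, because the SD of 15 means runs slightly low.

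An error SD of 8 is far from the plan's hypothesis that over 90% of readings fall within tolerance: with no bias it puts about 47% within ±5. An SD of 5/1.645 = 3.04 puts 90% within ±5. Scaling by 3.04/8 = 0.38 gives about 0.5 pooled, against 0.7, 1.0 and 1.2.

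**Unpaired pooled t-test, true bias 3 mmHg, error SD 8 (sim).** Detection rates:

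| ICC | Unpaired, BP SD 10 | Unpaired, BP SD 15 | Unpaired, BP SD 20 | Patient means |
|---|---|---|---|---|
| 0.1 | 59% | 26% | 7% | 87% |
| 0.3 | 58% | 31% | 13% | 60% |
| 0.5 | 56% | 35% | 17% | 45% |

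Two faults act in opposite directions. Ignoring pairing inflates the error variance and ignoring clustering deflates it. On a common scale (×1/150), the test uses 2 × (between² + 5²) + 8² = 314, 564 or 914 at BP SD 10, 15 or 20. The correct value is 64 × design effect = 122, 237 or 352. At BP SD 10 and ICC 0.5, 314 is below 352. The higher detection there comes from an error variance that is too small, not from a better test.

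**Bland-Altman (sim).** The pooled SD is 0.997, 0.991 and 0.986 of the true total SD, so the point limits barely move. A pooled 95% interval for a limit covers 90%, 79% and 66%; a clustered interval covers 96%.

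**Percentage within ±5, error SD 3.04, true 90% (sim).** The ICC of the yes/no indicator is only 0.01, 0.06 and 0.16. A pooled Wilson interval covers 96%, 90% and 82%: no harm at an error ICC of 0.1, modest at 0.3, clear at 0.5.

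**The case against.** The strongest reply is that little turns on this. Success is decided by the ISO mean and SD, and those formulas are not at fault here. The study is a 15-patient pilot, and the plan states no alpha and promises no confidence interval, so the error rates and widths above belong to tests and intervals that an analyst would have to supply. All of that stands, and it is why the point is minor.

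It is also fair that the gap is in the Section 9 list and not throughout: Section 9.3.3 does name paired determinations for the ISO mean and SD. But it pools them without a patient term, so it does not deal with the correlation. The t-test could be meant as paired, or for something other than wristband against A-line. The text does not say. In a single-arm study, in a paragraph that opens with data from the two devices, that comparison is the natural reading, but it remains an inference.

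A reader might infer three stronger things that the documents do not support:

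- That the pass or fail result is invalid. It is not affected.
- That an unpaired test always loses most of its power. This depends on assumed SDs and fails at a between-patient SD of 10 for the higher ICCs.
- That the plan takes a non-significant difference or a high correlation as proof of accuracy. It says neither, and it lists agreement separately from correlation.

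**Conclusion.** The point holds, as a minor one. The Section 9 tests have no stated pairing or unit, and nothing in the plan accounts for within-patient correlation. Run on pooled pairs, a nominal 5% paired t-test would give a false bias signal roughly three to eight times as often as intended over the assumed ICC range. Pooled intervals for mean error would be about 1.5 to 2.5 times too narrow (1.9/1.3 to 3.2/1.3). An unpaired test can lose much of its power when blood pressure varies widely between patients (assumed SD 15 to 20). At SD 10 it loses little at ICC 0.3 and shows no loss at 0.5.

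The ICC drives all of this and the documents give none; at zero correlation the pooled paired analysis would be sound. The harm is confined to the supporting tests and to any intervals reported with them.

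**What to change.** In Section 9, replace the t-test and chi-squared test, as wristband-against-A-line comparisons, with a paired analysis that takes the patient as the unit or cluster:

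1. Report mean systolic and diastolic error with a 95% interval from the 15 per-patient mean errors (t, 14 df), or from a model with a patient random intercept.
2. Use repeated-measures Bland-Altman limits on the raw paired differences, not on the zero-banded errors of Section 9.3.1, with intervals that allow for clustering.
3. Give any interval for the percentage within tolerance a patient-clustered variance, as description only.
4. Label the regression descriptive.

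Keep the ISO mean and S_n as the pass or fail rule.

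The cost is some wording and a few lines of code, with no extra patients or readings. The downside is wider intervals: besides those shown for mean error, the half-width for a limit of agreement goes from 2.2 to 2.9, 4.0 or 5.1 mmHg at an assumed error SD of 8 and ICC 0.1, 0.3 or 0.5.

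### Sections 9 and 9.3.1 score device error against two different A-line bands with no stated precedence, and the lateral-difference adjustment is never written into the error rule

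*Combined protocol and SAP*

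**What the plan says.** **Section 9, opening text.** "The data point is defined as the interval between the lower and higher value read by the A-Line", provided the window lasts at least 30 seconds and the range stays below 20 mmHg (SYS) or 12 mmHg (DIA). "Should the LiveMetric device read within the same range as the A-line, then the reading is considered accurate". Otherwise "the error rate is defined as the range in mmHg between the closest edges of the reference reading" and the wristband value. No sign is given.

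**Section 9.3.1.** "The reference SYS is defined as the range of a ± 1 experimental standard deviation around the mean value" of the invasive beats in the window; DIA is defined the same way. A wristband value inside that band has error 0. For a value outside it, the instruction is to "subtract the value of the determination from the adjacent limit of the range of the variation of BP", which is a signed difference. The section closes by taking the mean and SD of these errors.

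**Section 9.3.3.** The mean and SD formulas use each "individual paired determination of the LiveMetric device as determined above for all subjects". The error term "is the error of the ith individual determination as determined in" a section whose reference did not resolve. The same section states: "The lateral difference will be calculated initially as the average difference between the readings or determination made on each limb". Its formula is the mean of three readings on the wristband limb minus the mean of three on the reference limb.

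**Section 4.1.** The wristband goes on the limb opposite the A-line. The lateral difference is measured so that the calculation can be adjusted later, and subjects above 15 mmHg (SYS) or 10 mmHg (DIA) are excluded. Step 3 of the study schematic instead has the band worn on one wrist and then the other.

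**The concern.** Section 9.3.4 makes the ISO criterion for SYS and DIA the primary endpoint. Section 9.3.3 says that a mean or SD out of range obliges a change to the algorithm and a repeat on new data. Both depend on the error of each reading, which the plan defines in two ways. An analyst could choose between them after seeing the data and point to plan text for either choice.

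The lateral difference raises a separate problem. The wristband and the A-line are on different arms, so a true pressure difference between arms enters every comparison. If 9.3.1 and 9.3.3 are followed as printed, that difference is counted as device error. It adds between-patient spread, and it shifts the mean unless it averages zero. The schematic's two-wrist procedure also leaves unclear which readings an adjustment would apply to.

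**Working it through.** **The plan's own figure.** 15 patients × up to 10 readings = 150, the total in Section 9.5. It has no bearing on which band applies.

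**One reading under both rules (illustrative).** A-line mean 120, SD 4, minimum 111, maximum 129; wristband 127 mmHg. The range is 18, below the 20 mmHg cap, so the window is valid.
- Section 9: 127 lies in 111–129, so the error is 0.
- Section 9.3.1: the band is 116–124, so the error is 124 − 127 = −3 mmHg.

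**Direction.** An SD with divisor n cannot exceed half the range. If Section 9 means minimum to maximum, its band is therefore never materially narrower than mean ±1 SD. For normal beats the expected range is 4.09, 4.32 and 4.50 SD at 30, 40 and 50 beats, against 2 SD in 9.3.1.

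**Size.** The documents give no beat or device SD. Assumptions: 40 independent normal beats per 30 s, beat SD 3, device SD σ = 10, bias 0 (mmHg). For a band of half-width c:
- share with zero error = 2Φ(c/σ) − 1
- mean squared error = 2[(σ² + c²)(1 − Φ(c/σ)) − cσφ(c/σ)]
- mean absolute error = 2[σφ(c/σ) − c(1 − Φ(c/σ))]

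Section 9.3.1, c = 3: zero-error share 0.236. Mean square 2[109 × 0.3821 − 30 × 0.3814] = 60.4, so SD 7.8. Mean absolute error 2[3.814 − 1.146] = 5.3.

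Section 9, c = 12.9/2 = 6.45: zero-error share 0.481. Mean square 2[141.6 × 0.2595 − 64.5 × 0.3240] = 31.7, so SD 5.6. Mean absolute error 2[3.240 − 1.674] = 3.1.

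These formulas hold the band width fixed. Simulating 100,000 windows, with the width varying and windows over the cap dropped, gives:

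| | Section 9 | Section 9.3.1 |
|---|---|---|
| Band width, mmHg | 12.9 | 6.0 |
| Zero error | 48% | 24% |
| Error SD, mmHg | 5.7 | 7.8 |
| Mean absolute error, mmHg | 3.2 | 5.3 |
| DIA error SD (beat SD 2, device SD 8) | 5.0 | 6.5 |
| Mean error, bias 5, device SD 8 (device minus limit) | 2.3 | 3.6 |

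About 48 − 24 = 24% of readings are accurate under one rule and in error under the other. The error SD is 1 − 5.7/7.8 = 27% lower under Section 9. Over 30–50 beats, beat SD 2–4 and device SD 8–12, it is 14–43% lower. At bias 5 the mean error ranges over 1.6–3.2 (Section 9) against 3.2–4.1 (9.3.1).

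**Lateral difference (LD), scored by 9.3.1.** Assumptions: LD SD 5, device SD 8, beat SD 3, 15 patients × 10 readings, patients beyond 15 mmHg excluded. Left in, the spread before banding is √(8² + 5²) = 9.4. Removed exactly, it is 8. Estimated from three readings per limb with reading SD r, it is √(8² + 2r²/3), which is 8.2 at r = 2 and 8.4 at r = 3. Error SD by simulation:

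| Device SD | LD left in | LD removed (exact, or estimated with r = 2–3) |
|---|---|---|
| 5 | 4.8 | 3.0–3.5 |
| 8 | 7.1 | 5.8–6.2 |
| 10 | 8.9 | 7.8–8.1 |

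If LD averages 0, the mean error stays at 0. If LD averages 5 (device SD 8), the mean error is about 3.6 unadjusted and 0.0–0.1 adjusted.

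**The case against.** The operative rule can be inferred. Section 9.3.1 carries the title on determining the reference, gives both scoring rules and ends with the mean and SD; 9.3.3 then refers back to what was determined above. Section 9 can be read as loose introductory text that sets the window and the stability screen, and its lower and higher values might even mean the ±1 SD limits. This reading is reasonable and favours 9.3.1. It does not withdraw the Section 9 rule, which still says when a reading counts as accurate and how its error is measured, and the pointer that would settle the matter does not resolve.

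On the lateral difference, 4.1 states the intention to adjust, the exclusion limits cap the problem, and 9.3.3 defers to ISO formulas that may contain the step. That is fair. The intention is clear, but the step and its sign are not printed, and the standard cannot be checked from these documents.

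The sizes rest on assumptions. With beat autocorrelation 0.8 the base case becomes 6.3 against 8.0 mmHg (21% lower), and at beat SD 1 the reduction is about 9%. The direction does not change.

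Withholding device output from staff during measurement and using an independent biostatistician reduce the risk of a convenient choice. Neither fixes the rule in advance.

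**Conclusion.** The point holds and must be fixed. The plan has two live definitions of its primary variable, with the text leaning towards 9.3.1 without saying so. It also promises a lateral-difference adjustment that its formulas omit. Across the main scenarios the choice of band changes the error SD by 14–43%. Omitting the adjustment adds roughly 1 mmHg to the error SD when LD has SD 5 and the device SD 8, and more if the device is more precise. These sizes depend on the assumed beat, device and inter-arm SDs and on reading Section 9 as minimum to maximum; the textual conflict does not. Whether the endpoint would pass under one rule and fail under the other cannot be determined, because the ISO limits are not in the documents.

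**What to change.** 1. In Section 9, delete the two sentences that define an accurate reading and its error. Keep 20/12 mmHg only as a stability screen on the reference, say which width it tests, and state that 9.3.1 governs. The width matters: at beat SD 5, about 33% of SYS windows pass if the cap applies to the minimum-to-maximum range, and about 100% if it applies to the 2-SD width.
2. In 9.3.1, write one rule. Adjusted value = wristband value − LD, for SYS and DIA separately, for readings on the limb opposite the A-line; this sign follows from the 9.3.3 formula. Error = 0 if the adjusted value lies within the A-line mean ±1 SD. Otherwise error = the signed difference from the nearest limit, in one stated direction. The SD and the absolute mean do not depend on the direction chosen.
3. In 9.3.3, repair the cross-reference so that the error term points to this rule.
4. Reconcile step 3 of the schematic with step 2 of 4.1 on which wrist is used.

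The cost is wording only, since the A-line recording and LD readings are already planned. Apparent accuracy will look less favourable than under the Section 9 band. The adjustment gains little where inter-arm differences are small and LD is noisy: with LD SD 3, reading SD 3 and device SD 8, the error SD is 6.2 against 6.4. The separate fixed-tolerance criterion in 9.1 and 9.2 (±5 and ±2.5 mmHg, over 90% of readings) is not resolved by this change.
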